9.8 Quality control

The organization that is responsible for the conduct of the study (ZEG) has implemented different quality assurance procedures for day-to-day work. Internal audits confirm that ZEG fully complies with GPP ('Guidelines for Good Pharmacoepidemiology Practices' issued by the International Society for Pharmacoepidemiology in 2007), GEP (Good Epidemiological Practice issued by the European Epidemiology Federation in 2007), GVP (Good pharmacovigilance practices issued by the EMA in 2012/2013), the ENCePP Code of Conduct, the Nuremberg Code and the Declaration of Helsinki. Additionally, ZEG has been audited three times by large pharmaceutical companies, without major issues being identified. For this study, as for all other studies conducted by ZEG, site audits in the participating local field organizations will be conducted by ZEG on a regular basis. This included organizational aspects as well as source data verification.

ZEG's internal standard operating procedures (SOPs) manual describes standardized working procedures to ensure high quality and compliance with all applicable guidelines. The SOPs are reviewed on an annual basis and updated where necessary to ensure that all processes are in line with legal compliance and integrity of data. ZEG also uses standardized

PASS – Safety of nomegestrol/estradiol: Study Protocol Version 4.0 20 JUN 2019

working procedures for the Safety Monitoring and Advisory Council (SMAC), the Blinded Adjudication Board and study-specific working procedures for the local organizations.

All processes that are relevant for legal compliance of the study or the integrity of the data are subject to quality control measures. This includes 1) development of study protocol, questionnaires, databases and data entry screens, 2) data entry, 3) plausibility checks, 4) validation of clinical outcomes, 5) adverse outcome reporting, 6) data analysis, 7) report writing, 8) publication of results, 9) archiving of study materials (i.e. all baseline/follow-up questionnaires, other study documents and electronic files). All quality control measures are based on the four-eye principle (i.e., it is not sufficient that someone controls his/her own work). During study conduct the consistency between ZEG's electronic database and the original questionnaire will be audited several times by an external auditor.

The external auditor is also responsible for a systematic review of quality standards implemented at ZEG and the local organizations, as well as proposing suitable measures to ZEG management to improve quality standards.

ZEG's study work will be overseen for the whole study period by the Safety Monitoring and Advisory Council of internationally acknowledged experts in the field (cf. Section 10.3). This committee will take final decisions in all scientific matters.

9.9 Limitations of the research methods

In non-experimental studies like this prospective cohort study, the possibility of bias and residual confounding can never be entirely eliminated, and the ability to infer causation is correspondingly limited [6]. Valid information on potential sources of confounding and sophisticated statistical and epidemiologic methodology help to reduce the impact of bias and residual confounding [7]. However, the difficulty remains unresolved when all that exists is a weak association [8;9]. Relative risk estimates that are close to unity may not allow differentiation between causation, bias and confounding [10;11]. In general, it is difficult to interpret a relative risk of two or less in observational research [12;13].

Within these limitations of non-experimental studies the chosen study design is capable of minimizing bias and residual confounding. In our judgment, selection bias will not be a major issue in this study because the adverse events will be captured for in- and out-patients, and the demographic characteristics of the participants will be representative for adult OC users [1]. Also, misclassification bias will probably have no substantial impact on the results as precise information on the exposure and the

PASS – Safety of nomegestrol/estradiol: Study Protocol Version 4.0 20 JUN 2019

outcomes of interest will be available. In addition, reliable information on duration of current COC use will be available. Accordingly, the study will capture the well-known increased VTE risk during the first months of combined OC use [14;15;16]. Furthermore, the comprehensive follow-up procedures will ensure a low loss to follow-up rate. In theory, a disproportionately high percentage of SAEs (including VTE and ATE) could occur in those patients who are lost to follow-up, because SAEs could be the reason for the break in contact with the health care professional who prescribed their COC. An advantage of the study design, however, is that the investigator team will have direct contact with the participants; contact will not be lost if the women change health care professionals, for example (e.g., due to change of residence or dissatisfaction with treatment).

In contrast, it will be impossible to exclude diagnostic bias. Clinical symptoms of VTE cover the spectrum from a complete absence or unspecific, slight symptoms to dramatic, acute, life-threatening symptoms [17;18;19]. A high awareness of potential cardiovascular risks of combined oral contraceptive use may lead to more diagnostic procedures and, therefore, to more detected VTE. It is conceivable that this potential bias lead to an overestimate of the relative risk of a new product (such as NOMAC-E2) cohorts compared to the LNG-cohort. Therefore, diagnostic bias should not result in an underestimate of the VTE risk carried by NOMAC-E2.

Unlike in many other observational studies on hormonal contraceptives, a strength of the study will be the availability of information on many important prognostic factors for the outcomes of interest. Nevertheless, we acknowledge that due to the non-interventional character of the study, information on specific gene mutations will only be available for VTE cases but not for the vast majority of study participants who will not experience a VTE. This limitation will be mitigated through information on family history of VTE which has a higher predictive value for VTE compared to gene mutations [20].

This study combines several methodological strengths that are substantial for the validity of the results: i) prospective, comparative cohort design; ii) availability of important confounder information (e.g., BMI and family history of VTE); iii) validation of outcomes of interest and the exposure of the relevant cases; iv) comprehensive follow-up procedure and very low loss to follow-up to minimize underreporting; v) independent, blinded adjudication of VTE cases; vi) relevant statistical analyses (e.g., stratified analyses by user status and exposure period; comparison of isochronous, new user cohorts; sensitivity analyses on the impact of the adjudication process, outcome definition, and prognostic factor/covariate selection); vii) study population representative for oral contraceptive users under routine clinical conditions; viii) generalisability of results as COC use in this study reflects routine clinical use and

PASS – Safety of nomegestrol/estradiol: Study Protocol Version 4.0 20 JUN 2019

study participation is not limited by medical inclusion and exclusion criteria; ix) supervision by an independent Safety Monitoring and Advisory Council, and scientific independence from the study funder.

The study timelines given by the European regulatory authorities are very challenging. This means that the last regular follow-up and the end of recruitment have to be scheduled for September 2020 and September 2019, respectively.

9.10 Other aspects

9.10.1 Validation of self-reported events

Under routine medical conditions, diagnosis of an SAE is not always confirmed by a diagnostic method with high specificity. Therefore, SAEs will be classified by the investigator team as "confirmed" or "not confirmed" according to the following predefined algorithm:

• Definite Event:

Confirmed by diagnostic measures with high specificity (e.g., phlebography for DVT, spiral CT for pulmonary embolism, cerebral MRT for cerebrovascular accidents, ECG with typical ST segment elevation for acute myocardial infarction, histology for gynecological cancer, two-sided blood pressure measurement with diastolic blood pressure of more than 120 mmHg for hypertensive crisis)

• Probable Event:

Absence of confirmation by a diagnostic measure with high specificity, but clinical diagnosis confirmed by a health professional or supported by diagnostic tests with low specificity (such as D-dimer for VTE or typical ECG/blood gas tests for PE). These cases are usually characterized by a subsequent specific therapy (such as fibrinolysis or long-term anticoagulant therapy). However, if the attending physician confirms that the diagnosis is correct, the event will be classified as a probable event even if specific treatment was not given.

- Event not confirmed:
 - Diagnosis reported by the patient is excluded by diagnostic procedures
 - A different medical condition is diagnosed by the attending physician
 - The woman did not contact a health professional to clarify her symptoms and no diagnostic measures were performed that could have clarified the diagnosis

The exposure data reported by the patients will be validated via the prescribing physicians. Definite and probable events will be classified as 'confirmed events'.

For VTE, the definition of "definite", "probable" and "not confirmed" is further specified:

- **Definite VTE:** Confirmed by imaging procedure
 - DVT: phlebography, duplex sonography, magnetic resonance imaging
 - PE: pulmonary angiography, ventilation-perfusion scan, spiral computed tomography, magnetic resonance imaging, transesophageal echocardio-graphy

• Probable VTE:

Absence of confirmation by an imaging test, but a clinical diagnosis was confirmed by a health professional or is supported by a non-imaging test (such as ultrasound doppler, plethysmography, D-dimer for VTE or typical ECG/blood gas tests for PE). These cases are usually characterized by a subsequent specific therapy (such as fibrinolysis or long-term anticoagulant therapy). However, if the attending physician confirmed that the diagnosis is correct, the event was classified as a VTE, even if a specific treatment was not given.

- VTE not confirmed:
 - VTE excluded by a physician
 - A different medical condition was diagnosed by the attending physician
 - Woman did not contact a health professional to clarify her symptoms and no diagnostic measures were performed that could have clarified the diagnosis

For the final analysis this classification will be verified by means of an independent blinded adjudication process (cf. Appendix 3).

For ATE, the definition of "definite", "probable" and "not confirmed" Is further specified as follows:

- **Definite ATE**: Confirmed by a diagnostic method with high specificity (incl. intraoperative or post-mortem)
 - AMI: typical change of cardiac enzymes with high specificity (CK-MB, cardiac troponin, glycogen phosphorylase isoenzyme BB), typical ECG changes (e.g., ST-segment elevation), coronary angiography
 - Stroke: typical clinical signs persisting for days, confirmation by imaging with high specificity (e.g., CT, MRI, cerebral angiography, PET)

PASS – Safety of nomegestrol/estradiol: Study Protocol Version 4.0 20 JUN 2019

- TIA: typical clinical signs (followed by resolution within 24 hours) and imaging with high specificity and sensitivity (e.g., MRI) does not indicate tissue necrosis
- Other organs and peripheral arteries (e.g. kidney, gut, adrenals, femoral artery): confirmed by imaging with high specificity (e.g., arteriography, CT, MRI)
- **Probable ATE**: No confirmation by a diagnostic method with high specificity, but other evidence pointing in the direction and the clinical diagnosis is confirmed by attending physician
 - AMI: typical clinical symptoms, change of cardiac enzymes with low specificity (e.g., CK, AST, LDH) or indirect ECG signs (e.g., ST-segment depression in case of posterior myocardial infarction), and clinical diagnosis confirmed by attending physician
 - Stroke: clinical signs persisting for days, confirmatory imaging not done or inconclusive, but clinical diagnosis confirmed by attending physician
 - TIA: typical clinical signs, followed by resolution within 24 hours, but no imaging with high specificity; and the clinical diagnosis is confirmed by attending physician
 - Other organs and peripheral arteries (e.g. kidney, gut, adrenals, femoral artery): confirmatory imaging not done or inconclusive, but clinical diagnosis confirmed by attending physician
- ATE not confirmed:
 - ATE excluded by a physician
 - A different medical condition was diagnosed by the attending physician
 - Woman did not contact a health professional to clarify her symptoms and no diagnostic measures were performed that could have clarified the diagnosis

9.10.2 Blinded adjudication

The following adjudication procedure will be established:

- 1) Independent adjudication by the individual specialists
- 2) Documentation of the individual assessments
- 3) Comparison of the individual assessments
- 4) Discussion of "split decisions" among the adjudicators without enforcement of a unanimous decision

PASS – Safety of nomegestrol/estradiol: Study Protocol Version 4.0 20 JUN 2019

- 5) Independent re-adjudication of the discussed cases by the individual adjudicators
- 6) Documentation of the individual post-discussion assessments

Based on this procedure six different classification strategies will be possible

- Classification of the reported event as confirmed if all adjudicators classify the event as confirmed before the discussion of "split decisions" took place (i.e., the decision is based on step 2 of the six-step procedure described above)
- II. Classification of the reported event as confirmed if all adjudicators classify the event as confirmed after discussion of "split decision" takes place (i.e., the decision is based on step 6 of the six-step procedure described above)
- III. Classification of the reported event according to the assessment of the majority of adjudicators before the discussion of "split decision" takes place (i.e., "majority vote" based on step 2 of the six-step procedure described above)
- IV. Classification of the reported event according to the assessment of the majority of adjudicators after discussion of "split decision" takes place (i.e., majority classification based on step 6 of the six step procedure described above)
- V. Classification of the reported event as confirmed if at least one adjudicator had classified the event as confirmed before the discussion of split decisions took place (i.e., "worst case decision" based on step 2 of the six-step procedure described above)
- VI. Classification of the reported event as confirmed if at least one adjudicator had classified the event as confirmed after the discussion of split decisions took place (i.e., "worst case decision" based on step 6 of the six-step procedure described above)

The final analysis will be based on strategy V (worst case decision without discussion of split decisions) because it represents the most conservative approach. Alternative analyses will be possible on request of the Safety Monitoring and Advisory Council or regulatory authorities.

PASS – Safety of nomegestrol/estradiol: Study Protocol Version 4.0

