9.5 Study size

The sample size considerations are based on the expected VTE incidence for COC_{LNG}.

. It is expected that NOMAC-E2 is associated with a VTE risk that is not higher than the risk associated with COC_{LNG}.

The study should be powered to test non-inferiority of NOMAC-E2 treatment regarding VTE risk in comparison to COC_{LNG} use. Sample size calculations for a non-inferiority test of two exponential survival curves [4;5] showed that an expected number of 150 VTE cases should be sufficient to reach this goal. These calculations are based on the following assumptions: 1) one-sided α of 0.05; 2) power (1- β) of 0.80 and 3) non-inferiority limit on hazard ratio of 1.5.

At an incidence rate of 10.0/10,000 WY a total of 150 VTE cases could be expected within 150,000 WY. The drop-out rate in similar studies has been approximately 0.7% per month. Assuming 1) a recruitment phase of 36 months, 2) a follow-up phase of 12 - 24 months, and 3) a loss to follow-up rate of about 5%, follow-up of 101,000 study participants (50,500 NOMAC-E2 users and 50,500 COC_{LNG} users) for up to 24 months would result in approximately 150,000 WY (see table 1).

Based on these scenarios, the study is sufficiently powered to exclude a 1.5-fold VTE risk for NOMAC-E2 users compared to COC_{LNG} users in the event that the true VTE risk among NOMAC-E2 users is not higher than among COC_{LNG} users.

However, precise power calculations based on actual incidences and drop-out rates should be done on the basis of follow-up data 1) before the end of the recruitment phase and 2) after availability of 30,000 WY of observation. If these calculations do not confirm the assumed incidence and drop-out rates the Safety Monitoring and Advisory Council will discuss the need to decrease or increase the number of study participants and/or follow-up times.

²² 'idiopathic' pulmonary embolism and deep venous thrombosis of the lower extremities

PASS – Safety of nomegestrol/estradiol: Study Protocol Version 4.0 20 JUN 2019

The sample size needed for the investigation of the VTE risk is also sufficient for the evaluation of secondary outcomes – except ATE. Acute myocardial infarction and stroke are very rare in a female population of reproductive age. This study is powered to exclude a 2.5-fold risk of ATE. This is sufficient to screen for safety signals and substantial effects.

Table 1: Expected observation time

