9.7 Data analysis

Based on available data and pharmacological considerations the *a priori* assumption is that use of NOMAC-E2 is not associated with an increased risk of VTE compared to COC_{LNG}. That is, a statistical comparison of NOMAC-E2 and COC_{LNG} is not expected to show a difference. Therefore, the Principal Investigator and the Safety Monitoring and Advisory Council (cf. section 10.3) have chosen a non-inferiority design to investigate the VTE risk of NOMAC-E2. The primary analysis will be based on the comparison of the upper confidence limit for the point estimate of the VTE²³ hazard ratio with the predefined non-inferiority limit (see below).

²³ DVT of the lower extremities and pulmonary embolism, cf. Section 8

PASS – Safety of nomegestrol/estradiol: Study Protocol Version 4.0 20 JUN 2019

The final analyses will include both an "as treated" (AT) and an intention-to-treat (ITT) analysis using Cox regression models. The safety conclusions of the study, however, will be based on the AT analyses (outcomes of interest will be assigned to the treatment she used at the time of the event) because the ITT approach (outcomes of interest are assigned to the treatment which was prescribed at study entry) potentially dilutes differences between treatments.

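### Confirming a VTE on any single adjudicator's vote is conservative for absolute incidence, but not for the non-inferiority test on the hazard ratio that it is used for

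*Protocol*

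**What the plan says.** Under Section 9.2.5, three independent experts, blinded to the product used, adjudicate self-reported serious cardiovascular outcomes. Section 9.10.2 lists six ways to combine their votes: unanimous, majority or any single vote, each before or after discussion of split cases. It then chooses: "The final analysis will be based on strategy V (worst case decision without discussion of split decisions) because it represents the most conservative approach". The other strategies are offered there if the Safety Monitoring and Advisory Council or a regulator asks for them.

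Section 9.7 defines the test: "The primary analysis will be based on the comparison of the upper confidence limit for the point estimate" of the VTE hazard ratio with the margin of 1.5. Section 9.5 sets the design values: "one-sided α of 0.05" and power "of 0.80 and 3) non-inferiority limit on hazard ratio of 1.5". Power is claimed "in the event that the true VTE risk among NOMAC-E2 users is not higher than among" levonorgestrel users.

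Two other statements bear on the choice. Section 9.7 declines to base the safety conclusions on the intention-to-treat analysis because that approach "potentially dilutes differences between treatments". Section 9.9 lists sensitivity analyses on the adjudication process and on the outcome definition among the strengths of the study.

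**The concern.** A worst-case rule is conservative when the question is how many VTEs occur. The primary question is whether a ratio lies below 1.5. For a ratio, an equal loss of sensitivity in both cohorts mainly costs power. False-positive events at equal rates pull the ratio towards 1, and every added event narrows the interval. Both effects favour a finding of non-inferiority.

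The pool sent to the adjudicators does contain non-events. Section 9.2.5 says that laypersons often misclassify, and that rates of reported and validated events differ considerably.

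The protocol uses the dilution argument against intention-to-treat but does not apply it to the outcome rule. At stake is the one-sided 5% error of the main safety conclusion, which would rest on a rule described as cautious when, for this test, it probably is not.

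**Working it through.** **1. The plan's own figure.** Inputs from Section 9.5: margin 1.5, one-sided alpha 0.05, power 0.80, true hazard ratio 1; allocation about 1:1 (Section 9.2.2). Schoenfeld's formula gives events = 4 × (1.645 + 0.842)² / (ln 1.5)² = 150.4. With 150 events the power is 79.9%. The plan's 150 is reproduced.

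**2. Strategy V is the widest set.** V takes every unanimous yes and every split case. Only split cases are discussed and re-adjudicated, so no unanimous no can become a yes later. The case sets of strategies I, II, III, IV and VI therefore all lie inside V.

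**3. Effect of false positives on the test.** The protocol gives no error rates, so the shares are assumptions. Let f be the share of confirmed events in the levonorgestrel cohort that are false, with false positives at the same rate in both cohorts. At a true hazard ratio of 1.5:

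- expected ratio = 1.5 × (1 − f) + f
- SE(ln HR) = 2/√150 = 0.163
- chance of declaring non-inferiority = Φ[(ln 1.5 − ln expected ratio)/0.163 − 1.645]

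| f | expected ratio | chance |
|---|---|---|
| 0 | 1.50 | 5% |
| 10% | 1.45 | 7.5% |
| 20% | 1.40 | 11% |
| 30% | 1.35 | 16% |

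This holds the number of confirmed events at 150. If false positives are instead added to 150 true events, and the share is taken over all confirmed events, shares of 10%, 20% and 30% give 8.4%, 13.9% and 22.7%.

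**4. How much belongs to V.** The shares in step 3 are totals. A wrong diagnosis that all three readers accept counts under every strategy. If, for example, f were 5% under majority vote and 10% under V, the formula gives about 6.2% against 7.5%. The increment from V is then 1.3 percentage points.

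A direct comparison needs a model of the readers. Assume three independent readers, 150 true VTEs, and non-VTE reports split equally between the cohorts. One case in full: sensitivity 0.90, specificity 0.90, 150 non-VTE reports.

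- V accepts a non-VTE with probability 1 − 0.9³ = 0.271, so about 41 false events; expected ratio 1.37, error 14.8%.
- III accepts one with probability 3 × 0.1² × 0.9 + 0.1³ = 0.028, so about 4 false events; expected ratio 1.48, error 5.8%.

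Over sensitivity 0.85 to 0.95, specificity 0.90 to 0.95 and 75 to 300 non-VTE reports:

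| Strategy | error at true ratio 1.5 | power at true ratio 1 |
|---|---|---|
| I (unanimous) | 5.0–5.1% | 62–74% |
| III (majority) | 5.1–6.6% | 78–81% |
| V (any one) | 7.0–29% | 82–92% |

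Readers of the same records probably make correlated errors, which would narrow the gap between V and III.

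**5. When the direction changes.** If false positives fall NOMAC-E2 to levonorgestrel in ratio g, the expected ratio becomes 1.5 × (1 − f) + f × g, which equals 1.5 at g = 1.5. With false positives at 20% of all confirmed events, added to 150 true events, the error is 13.9% at g = 1, 8.1% at 1.25, 5.0% at 1.5 and 2.2% at 2.

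**The case against.** Much of the case for the plan stands, and it limits what can be claimed.

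- **Absolute risk.** The primary objective in Section 8 includes an estimate of absolute risk. For that, V is conservative, so the label has a basis.
- **Alternatives.** From Section 9.10.2 a reader might infer that stricter rules run only if someone asks. Section 9.9 does not support that, since it already names sensitivity analyses on adjudication and outcome definition, and Section 9.7 leaves sub-analyses to the statistical analysis plan. What remains is that Section 9.9 names no strategy, that the two sections differ in firmness, and that the primary result rests on V.
- **Differential false positives.** Blinding equalises reader error per report, not the number of reports per cohort. Section 9.9 expects a new product may attract more diagnostic work-up. That passage concerns more detected VTE, however, and nothing in the protocol establishes false confirmations 1.5 times as frequent under NOMAC-E2.
- **Real VTE among split cases.** If all the added cases were true events, the ratio would not be biased. V would still give the narrowest interval, so it would not be the cautious choice.
- **Probable VTE.** A reader might add to the charge against V that "Definite and probable events will be classified as" confirmed, where a probable VTE is defined by "Absence of confirmation by an imaging test, but a clinical diagnosis was confirmed by a health professional or is supported by a non-imaging test". That definition applies before any voting rule is chosen, and Section 9.10.1 says such cases usually received specific therapy. It is a separate question.

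**Conclusion.** The rationale in Section 9.10.2 is right for absolute incidence and wrong for the hazard-ratio test. V contains the case sets of the other five strategies. With false positives about equally frequent in both cohorts, which blinding makes the natural assumption for reader error, it dilutes the ratio and narrows the interval.

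The documents do not fix the size. The 7.5% to 16% rests on assumed total false-positive shares of 10% to 30%; a reader might take it as the effect of V, but V accounts for only part of it. The 7.0% to 29% in the reader model rests on independent errors and assumed report counts. Nor do the documents support calling V the least conservative rule without condition, because the effect vanishes at a false-positive ratio of 1.5 and reverses above it.

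**What to change.** 1. In Section 9.10.2, delete the conservative rationale as far as it concerns the hazard-ratio test.
2. Make strategy III (majority vote before discussion) the basis of the non-inferiority test. Alternatively, keep V and make III a mandatory pre-specified co-analysis whose upper limit must also lie below 1.5.
3. Report strategy I and definite-only VTE as pre-specified sensitivity analyses, without requiring that they also pass. Strategy I alone has 62% to 74% power in the reader model, so a joint requirement would be costly.
4. Keep V for absolute incidence.
5. Reconcile the on-request wording in Section 9.10.2 with the sensitivity analyses named in Section 9.9.

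No new data are needed: the individual pre-discussion votes are already documented in step 2 of the adjudication procedure. The cost is wording, extra runs of the same model, and slightly fewer events and lower power than under V (78% to 81% under III against 82% to 92% in the reader model, with 80% planned). If III is a co-analysis, the joint power cannot exceed that of III alone; it was not computed.
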